4. OVERALL STUDY DESIGN

4.1. Study Design

This is an open-label multicenter, Phase 2, Simon two-stage optimal design for targeted therapy study of single arm AL101 monotherapy in subjects with Notch-activated recurrent or metastatic TNBC whose disease has recurred or progressed after 3 or fewer lines of prior therapy.

The design will include a lead-in cohort with 6 subjects to ascertain safety of the investigational product (IP), AL101, 6 mg weekly (QW). The safety will be reviewed on a regular schedule (weekly calls with investigators, and quarterly reviews with the Data Monitoring Committee [DMC]). After the 6th subject is enrolled and completes 4 weeks of therapy (1 cycle), the results will be reviewed in aggregate and, if the safety is acceptable (as defined below), the study will continue at 6 mg administered QW. Note, if safety is not acceptable amongst the first 6 subjects dosed at 6 mg QW, the IP dose will be reduced to 4 mg QW. The decision on which dose to use for the remainder of the study will be determined after formal safety assessment with the investigators and the DMC.

Acceptable safety:

- 2 or fewer subjects experience Grade 3 or 4 diarrhea lasting more than 3 days
- 2 or fewer subjects experience another specific Grade 3 or 4 adverse event (AE) which is attributable to IP

After the lead-in phase with AL101 6 mg QW, the study will proceed to complete the described Simon two-stage design as shown in [Figure 1](#) and described in Section [9.1](#).

Prior to entering the study, to determine eligibility, potential candidates who sign a separate pre-screening informed consent, will undergo pre-screening assessment for evaluation of Notch mutational status from a persistent locally advanced or metastatic lesion. If historical genotyping results from the last 2 years that identify a Notch-activated genetic alteration are available from a commercially available NGS assay or laboratory developed test (LDT), these results are acceptable to use for determining eligibility. In Europe any commercially available CE marked device can be used.

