	
 Evaluate subject carefully including laboratory assessments (chemistry, liver function tests and lipase) Loperamide 4 mg at the first onset of diarrhea, then 2 mg every 2 hours around-the-clock until diarrhea free for at least 12 hours. Subjects may take loperamide 4 mg every 4 hours during the night. These doses should not be used for more than 48 hours due to the risk of paralytic ileus. For subjects that cannot tolerate loperamide or do not get adequate relief with maximum doses, standard doses of LOMOTIL® (diphenoxylate/atropine) may be added or used instead of loperamide. Additional antidiarrheal measures, such as octreotide, may be used at the discretion of the investigator or treating physician 
If the above measures have not worked, or subject has progressed to Grade 2, or after Grade 1 with no improvement within 3 days with maximum doses of loperamide:
 
 Subject may be treated with dexamethasone at a dose of 8 mg every 8 hours (Q8h) for up to 5 days. If still no improvement in symptoms, the subject may continue with the dexamethasone or consider switching to budesonide 9 mg once daily (QD). Refer to Section 6.6.2 for additional instructions on premedication with steroids. 	
 Evaluate subject carefully including laboratory assessments (chemistry, liver function tests and lipase) Loperamide 4 mg at the first onset of diarrhea, then 2 mg every 2 hours around-the-clock until diarrhea free for at least 12 hours. Subjects may take loperamide 4 mg every 4 hours during the night. These doses should not be used for more than 48 hours due to the risk of paralytic ileus. For subjects that cannot tolerate loperamide or do not get adequate relief with maximum doses, standard doses of LOMOTIL® (diphenoxylate/atropine) may be added or used instead of loperamide. Additional antidiarrheal measures, such as octreotide, may be used at the discretion of the investigator or treating physician 
If the above measures have not worked, or subject has progressed to Grade 2, or after Grade 1 with no improvement within 3 days with maximum doses of loperamide:
 
 Subject may be treated with dexamethasone at a dose of 8 mg Q8h for up to 5 days. If still no improvement in symptoms, the subject may continue with the dexamethasone or consider switching to budesonide 9 mg QD. Refer to Section 6.6.2 for additional instructions on premedication with steroids.

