	
(diphenoxylate/atropine) may be added or used instead of loperamide.
 
 Additional antidiarrheal measures, such as octreotide, may be used at the discretion of the investigator or treating physician 
If the above measures have not worked, or subject has progressed to Grade 3:
 
 Treat with dexamethasone at a dose of 8 mg Q8h for up to 5 days. If still no improvement in symptoms, the subject may continue with the dexamethasone or consider switching to budesonide 9 mg QD. Refer to Section 6.6.2 for additional instructions on premedication with steroids. 
Dose modifications for AL01:
 
Interrupt AL101 until resolution to \leq Grade 1 (refer to Section 6.4.2 and above for management guidelines for diarrhea).
 
Change dose regimen to 6 mg 2 weeks on / 1 week off for the first episode.
 
Decrease AL101 dose to 4 mg QW for second episode and to 2.4 QW mg for third episode.
 
If the diarrhea does not resolve to Grade 1 by 14 days, the subject will be discontinued from IP (refer to Section 7.2 for handling IP discontinuation).
 
If treatment interruption is longer than 28 days, the subject will be discontinued from IP (refer to Section 7.2 for handling IP discontinuation).
	
(diphenoxylate/atropine) may be added or used instead of loperamide.
 
 Additional antidiarrheal measures, such as octreotide, may be used at the discretion of the investigator or treating physician 
If the above measures have not worked, or subject has progressed to Grade 3:
 
 Treat with dexamethasone at a dose of 8 mg Q8h for up to 5 days. If still no improvement in symptoms, the subject may continue with the dexamethasone or consider switching to budesonide 9 mg QD. Refer to Section 6.6.2 for additional instructions on premedication with steroids. 
Dose modifications for AL01:
 
Interrupt AL101 until resolution to \leq Grade 1 (refer to Section 6.4.2 and above for management guidelines for diarrhea).
 
Decrease AL101 dose to 2.4 mg QW.
 
If the diarrhea does not resolve to Grade 1 by 14 days, the subject will be discontinued from IP (refer to Section 7.2 for handling IP discontinuation).
 
If treatment interruption is longer than 28 days, the subject will be discontinued from IP (refer to Section 7.2 for handling IP discontinuation).

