6.4.2. Guidelines for Management of Diarrhea

The guidelines for the management of diarrhea are included in [Table 3](#) and are not meant to replace the clinical judgment of the investigator / treating physician(s) or an institutional diarrhea management protocol which adheres to most current medical standards.

1. Treat with loperamide

Loperamide should be started at the earliest sign of (1) a poorly formed or loose stool, (2) the occurrence of 1 to 2 more bowel movements than usual in 1 day, or (3) an increase in stool volume or liquidity. Loperamide may be taken in the following manners: 4 mg at the first onset of diarrhea, then 2 mg every 2 hours around-the-clock until diarrhea free for at least 12 hours. Subjects may take loperamide 4 mg every 4 hours during the night. This dosing regimen is higher than the standard dose of loperamide, but is typical for the treatment of diarrhea caused by anticancer therapy ([Real, 2009](#)). These doses should not be used for more than 48 hours due to the risk of paralytic ileus. Subjects should be provided with loperamide at the initial treatment visit so that they have sufficient supply on hand in case antidiarrheal support is required. It is important that loperamide is taken as instructed, as some cases of higher-grade diarrhea have occurred in subjects not taking the maximum doses, and these cases have improved after loperamide was taken more frequently. For subjects that cannot tolerate loperamide or do not get adequate relief with maximum doses, standard doses of LOMOTIL® (diphenoxylate/atropine) may be added or used instead of loperamide. Additional antidiarrheal measures, such as octreotide, may be used at the discretion of the investigator or treating physician.

2. Treat with dexamethasone

For Grade 2 or 3 diarrhea that is not adequately controlled with loperamide and dose interruption, administration of corticosteroid may be considered at the discretion of the treating physician/investigator. The subject may be treated with dexamethasone at a dose of 8 mg Q8 hours for up to 5 days. If there still no improvement in symptoms, the subject may continue with the dexamethasone or consider switching to budesonide 9 mg QD. Refer to Section [6.6.2](#) for additional instructions on premedication with steroids.

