6.6.3. Allowed Medications

All treatments that the investigator considers necessary for a subject's welfare may be administered at the discretion of the investigator in keeping with the community standards of medical care. All concomitant medication will be recorded on the eCRF including all prescription, over-the-counter (OTC), herbal supplements, and IV medications and fluids. If changes occur during the study period, documentation of drug dosage, frequency, route, and date may also be included on the eCRF.

All concomitant medications received within 28 days before the first dose of IP and 30 days after the last dose of IP should be recorded. Concomitant medications administered after 30 days after the last dose of IP should be recorded for SAEs and AESIs. In addition, all prior therapies for BC should be recorded as specified in Section 8.2.1.

Allowed concomitant therapies:

- Glucocorticoids (for instructions on premedication with corticosteroids refer to Section 6.6.2).
- In case of toxicity (e.g., GI AEs), per discretion of the investigator and in consultation with the Sponsor's Medical Monitor, dexamethasone (for example 4-8 mg every 6 hours for up to 72 hours, starting 12 hours before AL101 administration or per institution guidelines) will be permitted.
- Palliative radiation therapy to a limited field (e.g., painful bone metastasis, painful lumps), *if it is not the sole site of measurable and/or assessable disease*, is allowed any time during study participation with prior approval of the Sponsor's Medical Monitor.

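### The diarrhea rules in Table 3 and Section 6.4.2 conflict: a 3-day steroid trigger on loperamide doses capped at 48 hours, and dexamethasone for Grade 3 that is directed in one place and optional in the other

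*Combined protocol and SAP*

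**What the plan says.** **Loperamide.** Every diarrhea entry in Table 3 (Grades 1 to 4, both starting-dose columns) gives the same regimen: "Loperamide 4 mg at the first onset of diarrhea, then 2 mg every 2 hours around-the-clock", with a 4 mg every 4 hours option at night. Each adds the limit "These doses should not be used for more than 48 hours due to the risk of paralytic ileus". Section 6.4.2 repeats both and comments: "This dosing regimen is higher than the standard dose of loperamide".

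**Steroid triggers, Table 3 Grade 2 entry.** Three triggers are joined by *or*: the earlier measures have failed; the subject has reached Grade 2; "or after Grade 1 with no improvement within 3 days with maximum doses of loperamide". Any of them permits, but does not require, dexamethasone. The Grade 1 entry has no steroid step.

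**Dexamethasone for Grade 3.** Once the earlier measures fail or the subject reaches Grade 3, Table 3 says: "Treat with dexamethasone at a dose of 8 mg Q8h for up to 5 days". For Grade 2 or 3 diarrhea that loperamide and dose interruption have not adequately controlled, Section 6.4.2 says: "administration of corticosteroid may be considered at the discretion of the treating physician/investigator". Both give 8 mg every 8 hours for up to 5 days, and both allow continuation or a switch to budesonide.

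**Which text governs.** Table 3 refers to Section 6.4.2 for diarrhea management. Section 6.4.2 says that the guidelines are in Table 3 and do not displace clinical judgment or an institutional protocol.

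**The concern.** The first conflict lies within one table entry. Its steroid clause presupposes a longer time on maximum-dose loperamide than its safety limit allows, and the protocol itself names the hazard behind that limit. The second lies between two sections that a site would read together for the same Grade 3 event: one directs a steroid, the other leaves it optional and places it after two other measures.

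Diarrhea is the toxicity on which the dose rationale leans. Section 4.3 argues that 6 mg weekly is tolerable with proactive control, described as early, frequent loperamide and a readiness to move to steroids. Section 6.4.2's discretionary later step fits that description less well than Table 3's directive. If sites follow different sections, the protocol's main managed toxicity is handled unevenly across a small single-arm trial.

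**Working it through.** The plan gives no figure to reproduce. The check is a comparison of texts with unit arithmetic.

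**1. Loperamide limit against steroid trigger (Table 3, Grade 2 entry)**

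- Cap: 48 h. Trigger: 3 days × 24 h = 72 h.
- Excess: 72 − 48 = 24 h; ratio 72/48 = 1.5.
- Cumulative dose as written, 4 mg and then 2 mg every 2 h: at 48 h, 4 + 24 × 2 = 52 mg; at 72 h, 4 + 36 × 2 = 76 mg; difference 24 mg. The night option gives the same daily rate (4 mg × 6 = 24 mg per 24 h, against 2 mg × 12 = 24 mg).

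The documents do not define maximum doses. The capped regimen is the natural referent: it is the only loperamide regimen given, and Section 6.4.2 calls it higher than standard.

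Can a site comply with both statements? A subject with Grade 1 diarrhea at 48 h must stop the high-dose regimen. Other antidiarrheals are listed, and if the measures have failed, the first trigger permits steroids. That route respects the cap. What cannot be met literally within the cap is the third trigger.

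**2. Dexamethasone for Grade 3**

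| | Table 3, Grade 3 | Section 6.4.2 |
|---|---|---|
| Obligation | directed | discretionary |
| Precondition | earlier measures failed, or Grade 3 reached | not controlled with loperamide and dose interruption |
| Dose and duration | 8 mg every 8 h, up to 5 days | the same |

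A subject who has just reached Grade 3 meets Table 3's condition at once. Under Section 6.4.2 the same subject qualifies only after loperamide and interruption have proved inadequate, and then only at the physician's discretion. The cross-references run both ways and state no order of precedence.

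**3. Link to the lead-in decision**

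Section 4.1 treats safety as acceptable on this criterion if "2 or fewer subjects experience Grade 3 or 4 diarrhea lasting more than 3 days", among 6 subjects. The loperamide conflict concerns persistent Grade 1 and does not feed that count. The dexamethasone conflict concerns Grade 3 and could, if the timing of rescue changes how long an episode lasts. The documents give no figure for that effect, so no size can be attached.

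**The case against.** **The loperamide clause is harmless.** The cap appears in every diarrhea entry, nothing instructs a site to exceed it, the steroid step is permissive, and another trigger is available. The clause might also mean 3 days of observation with maximum doses only in the first 48 hours. Much of this stands: a reader might infer that sites are forced to choose between the cap and steroid rescue, and the documents do not support that. The contradiction in wording remains, because the softer reading is not written.

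**Section 6.4.2 defers to Table 3 and to clinical judgment.** It does point to Table 3, but Table 3 points back. The judgment sentence softens the practical effect without saying whether dexamethasone is expected for Grade 3. Table 3 already requires interruption for Grade 3, which narrows the gap in preconditions. But starting an interruption is not the same as finding that it has not given control.

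**Section 6.6.3 might look like a third, conflicting rescue regimen.** It permits "dexamethasone (for example 4-8 mg every 6 hours for up to 72 hours, starting 12 hours before AL101 administration", or institutional practice, in consultation with the Medical Monitor. It is an example timed to an infusion, whereas Table 3 withholds AL101 during Grade 2 or 3 diarrhea and stops it permanently for Grade 4. It may well be peri-infusion use after toxicity, so comparing its total dose with the rescue course is not like with like. The text does not state its purpose, which is worth a clarifying line.

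**The lead-in dose might seem to turn on these conflicts.** For the loperamide conflict it does not, since the grades differ. For the dexamethasone conflict the link is plausible but remote. Assume Section 4.3's Grade 3 diarrhea rates apply to the lead-in. At 19%, the chance of 3 or more of 6 is 20(0.19³)(0.81³) + 15(0.19⁴)(0.81²) + 6(0.19⁵)(0.81) + 0.19⁶ = 0.087, before any duration requirement. The same formula gives 0.0005 at 3% and 0.0007 at 3.4%, the percentages given for ACCURACY, and 0.0036 at that study's stated count of 2/34 (5.9%). The dose decision also follows a formal assessment with the investigators and the DMC.

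**Conclusion.** Two contradictions stand in the current text. In Table 3's Grade 2 entry, a steroid trigger for persistent Grade 1 diarrhea presupposes 72 hours on a loperamide regimen limited to 48. This rests on reading maximum doses as the capped regimen, and an alternative trigger keeps the instructions workable. For Grade 3 diarrhea, Table 3 and Section 6.4.2 agree on dexamethasone dose and duration but differ on whether it is required and what must come first.

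The consequence is inconsistent handling of the toxicity on which the dose rationale depends, with the loperamide limit tied to a named risk. No harm or change of lead-in dose is demonstrated. Reconciliation is warranted because the rules conflict as written and the correction is cheap.

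**What to change.** In the next amendment, reconcile the Table 3 diarrhea entries (both dose columns) with Section 6.4.2:

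- Make the loperamide time limit and the steroid trigger for persistent Grade 1 diarrhea compatible, and define what maximum doses refers to.
- Give the same obligation and the same precondition for dexamethasone in Grade 3 diarrhea in both places, or state which text governs.
- Optionally, state in Section 6.6.3 whether its dexamethasone example is peri-infusion use after toxicity or treatment of an episode.

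The sponsor decides which values and rules are correct; this review takes no position on them. The cost is amendment wording and a letter to sites, with no new procedures or subjects.

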
Dose Modification Criteria for AL101 -Related Adverse Events	AL101 modification at next dose	
	Dose 6 mg QW	Dose 4 mg QW
	
Dose modifications for AL01:
 
Interrupt AL101 until resolution to \leq Grade 1 (refer to Section 6.4.2 and above for management guidelines for diarrhea).
 
Change dose regimen to 6 mg 2 weeks on / 1 week off for first episode
 
Decrease AL101 dose to 4 mg QW for second episode and to 2.4 mg QW for third episode.
 
If the diarrhea does not resolve to Grade 1 by 14 days, the subject will be discontinued from IP (refer to Section 7.2 for handing IP discontinuation).
 
If treatment interruption is longer than 28 days, the subject will be discontinued from IP (refer to Section 7.2 for handing IP discontinuation).
	
Dose modifications for AL01:
 
Interrupt AL101 until resolution to \leq Grade 1 (refer to Section 6.4.2 and above for management guidelines for diarrhea).
 
Decrease AL101 dose to 2.4 mg QW.
 
If the diarrhea does not resolve to Grade 1 by 14 days, the subject will be discontinued from IP (refer to Section 7.2 for handing IP discontinuation).
 
If treatment interruption is longer than 28 days, the subject will be discontinued from IP (refer to Section 7.2 for handing IP discontinuation).

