If the diarrhea does not resolve to Grade 1 by 14 days, the subject will be discontinued from IP. If treatment interruption is longer than 28 days, the subject will be discontinued from IP (refer to Section [7.2](#) for handing IP discontinuation).

For Grade 4 diarrhea, the subject must be discontinued from IP (refer to Section [7.2](#) for handing IP discontinuation).

3. Interrupt AL 101 dosing

For Grade 2 or 3 diarrhea that is not controlled (i.e., to Grade 1) with loperamide, dosing of AL101 should be interrupted, as continued dosing is likely to result in increased severity of diarrhea. In addition, evaluation of infectious causes should be considered. Based on the mechanism of action and preliminary clinical experience, full gastrointestinal (GI) tract recovery will likely take longer than the time for diarrhea to resolve. Thus, interruption for 5 days to 7 days beyond the resolution of diarrhea should be considered. Depending on the severity, time to onset, and time to resolution of diarrhea, reduction of AL101 dose and/or frequency, omission of future doses, or corticosteroid co-administration should be considered (as outlined in Section 6.6.2). If the diarrhea does not resolve to Grade 1 by 14 days, the subject will be temporarily discontinued from IP. If IP interruption is longer than 28 days, the subject will be permanently discontinued from IP (refer to Section 7.2 for handling IP discontinuation).

4. Increase fluid intake and, if applicable, consider stopping antihypertensive therapy and nonsteroidal anti-inflammatory drugs

Hypotension and/or renal insufficiency can occur in the setting of volume depletion from severe diarrhea. At the onset of any diarrhea, subjects should be instructed to increase fluid intake to help maintain fluid and electrolyte balance during episodes of diarrhea. Parenteral hydration should be started if oral hydration is not sufficient. The investigator should consider interrupting antihypertensive therapy and nonsteroidal anti-inflammatory drugs, if medically appropriate.

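### For AL101-related Grade 2 and 3 diarrhea, Table 3, Section 6.4.2 item 3 and the Section 6.4 general text give different dosing rules, and no sentence says that Table 3 prevails

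*Combined protocol and SAP*

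**What the plan says.** Four places in the protocol bear on dosing after diarrhea.

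- **Table 3 (Section 6.4).** Its scope is "Dose Modification Criteria for AL101 -Related Adverse Events". For Grade 2 diarrhea, the dose-modification block in both dose columns orders interruption until Grade 1 or lower. At 6 mg QW it adds "Change dose regimen to 6 mg 2 weeks on / 1 week off for first episode", and at 4 mg QW "Decrease AL101 dose to 2.4 mg QW". For Grade 3 diarrhea at 6 mg QW it says "Change dose regimen to 6 mg 2 weeks on / 1 week off for the first episode". Diarrhea not down to Grade 1 by 14 days leads to discontinuation of the product.
- **Section 6.4.2 item 3.** "For Grade 2 or 3 diarrhea that is not controlled (i.e., to Grade 1) with loperamide, dosing of AL101 should be interrupted". Depending on severity and timing, "reduction of AL101 dose and/or frequency, omission of future doses, or corticosteroid co-administration should be considered". It also advises that "interruption for 5 days to 7 days beyond the resolution of diarrhea should be considered". Diarrhea unresolved at 14 days leads to a temporary stop, which becomes permanent after 28 days of interruption.
- **Section 6.4.2 item 2.** Corticosteroid may be considered for Grade 2 or 3 diarrhea "not adequately controlled with loperamide and dose interruption". At 14 days item 2 agrees with Table 3.
- **Section 6.4 general text.** It opens by locating dose modification in Table 3. It then says that Grade 2 toxicity that is easy to manage needs no dose reduction, that intolerable Grade 2 toxicity is decided case by case with the sponsor, and that drug-related non-hematological Grade 3 toxicity leads to a reduction by one dose level. A reduced dose may not be raised again.

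Section 6.4.2 opens by saying that the diarrhea guidelines are in Table 3 and do not replace clinical judgment or an institutional protocol. Table 3 refers back to Section 6.4.2 for diarrhea management.

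**The concern.** These are competing instructions for the same event. Take a first AL101-related Grade 2 episode that loperamide brings to Grade 1. A site following Table 3 changes the regimen. A site relying on item 3 could conclude that the condition for interruption was never met and that a reduction is optional. A site relying on the general text could conclude that no reduction is needed.

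The event is foreseeable. Section 4.3 lists diarrhea among the adverse events reported in more than 30% of treated subjects in the ongoing adenoid cystic carcinoma study, and the case for 6 mg QW rests on rigorous control of gastrointestinal toxicity. Section 8 allows no waivers, yet a site cannot tell from the text whether unchanged dosing after such an episode is a deviation. At stake is consistent dosing, and consistent prevention of recurrence, which the current amendment gives as the aim of the scheduled interruption.

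**Working it through.** There is no sample size or error-rate figure to reproduce. The check sets the texts side by side and then sizes the planned dose.

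**Step 1. The texts, for AL101-related events**

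| Question | Table 3 | Section 6.4.2 item 3 | Section 6.4 general text |
|---|---|---|---|
| Interrupt for Grade 2? | Yes, no loperamide condition | If not controlled with loperamide | No rule specific to diarrhea |
| First Grade 2 step | Mandatory: 6 mg QW to 2 weeks on / 1 week off; 4 mg QW to 2.4 mg QW | Reduction to be considered | No reduction if easily managed; case by case if intolerable |
| First Grade 3 step from 6 mg QW | Mandatory: 2 weeks on / 1 week off | Reduction to be considered | Mandatory: down one dose level |
| Unresolved at 14 days | Discontinue | Temporary stop | Not addressed |

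Table 3 does contain wording about measures that have not worked. In the Grade 2 row it introduces dexamethasone, and reaching Grade 2 is enough to satisfy it. It is not a condition on the dose block.

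**Step 2. Planned dose after a first Grade 2 episode**

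Inputs are the doses and schedules in Table 3 and the 8-week imaging interval in Section 4.1. The comparator is unchanged dosing, which is inferred from item 3. Formula: infusions in the period × dose per infusion.

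Per 3 weeks:
- 6 mg QW: 3 × 6 = 18 mg. With 2 weeks on / 1 week off: 2 × 6 = 12 mg. Change: 12/18 − 1 = −33%.
- 4 mg QW: 3 × 4 = 12 mg. At 2.4 mg QW: 3 × 2.4 = 7.2 mg. Change: 7.2/12 − 1 = −40%.

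Per 8 weeks:
- 6 mg QW: 8 × 6 = 48 mg. With 2 weeks on / 1 week off there are 6, 5 or 5 infusions, depending on where in the pattern the interval starts. That gives 36, 30 or 30 mg, on average 48 × 2/3 = 32 mg.
- 4 mg QW: 8 × 4 = 32 mg. At 2.4 mg QW: 8 × 2.4 = 19.2 mg.

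**Step 3. First Grade 3 episode from 6 mg QW**

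Taking one dose level below 6 mg to be 4 mg, as in Table 3's reduction steps, the general text gives 3 × 4 = 12 mg per 3 weeks. Table 3's schedule change also gives 2 × 6 = 12 mg. The planned average dose is therefore the same. What differs is the dose per infusion, the schedule, and the remaining steps: Table 3 still has 4 mg QW in reserve for a second episode.

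**Step 4. How many subjects**

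This cannot be calculated, because the documents give no Grade 2 diarrhea rate.

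**The case against.** The strongest reply is that the protocol already points to Table 3. Section 6.4 places dose modification there, Section 6.4.2 says the diarrhea guidelines are there, and Table 3's reference back is for management rather than dose steps. Its rows are specific to grade, dose and episode, so a site would ordinarily follow them. This stands, and it lowers the weight of the point. It does not remove the conflict, because item 3 addresses the same actions in softer terms and nothing ranks the texts.

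Second, the interruption rules may not diverge in practice. Table 3 describes the modification at the next dose, and dosing is weekly. If the episode reaches Grade 1 before the next infusion, Table 3 need not cost a dose; if loperamide fails, item 3 also interrupts. This stands too, and leaves the regimen step as the main difference.

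Third, the clinical-judgment sentence may mean that variation is intended, and the amendment's rationale speaks of allowing the 2 weeks on / 1 week off regimen. But Table 3 separates diarrhea management from dose modification, so that sentence may not reach the dose steps. If discretion is intended, Table 3's imperatives are what need changing.

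Fourth, the texts agree on Grade 4 and on the 28-day limit, and the weekly investigator calls in Section 4.1 offer a way to notice divergence. Both are true, but spotting divergence does not tell a site which rule applies.

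A reader might also infer that item 3 tells sites to continue unchanged once loperamide works. It does not; it is silent on controlled diarrhea.

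**Conclusion.** The inconsistency is real and the point holds, at minor to moderate priority. Table 3 is the likely governing text, but the protocol does not say so, and three texts give different rules for related Grade 2 and Grade 3 diarrhea, with a further mismatch at 14 days.

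The planned dose after a first controlled Grade 2 episode is 33% lower under Table 3 from 6 mg QW than with unchanged dosing. From 4 mg QW it is 40% lower, and that reduction cannot be reversed. The first figure rests on the inferred no-change reading. The second needs that reading and also a lead-in result that moves the study to 4 mg. The conclusion is limited to AL101-related events, because Table 3 is so limited and Section 6.4.2 is not.

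It may be tempting to go further and say that the mixed handling weakens Notch inhibition or biases the response rate. The documents do not support this. Section 4.3 compares weekly doses and gives no Hes1 or Hes4 data for 2 weeks on / 1 week off, and without a Grade 2 rate neither the number of subjects affected nor any shift in ORR can be derived.

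**What to change.** 1. In Section 6.4, state that for AL101-related diarrhea Table 3 governs interruption, modification and discontinuation, and prevails over the Section 6.4 general text and Section 6.4.2.
2. In the Section 6.4 general text, add an exception for what Table 3 specifies to the two Grade 2 sentences and to the Grade 3 dose-level sentence. This settles the first Grade 3 diarrhea step from 6 mg QW.
3. In Section 6.4.2 item 3, add that for AL101-related Grade 2 or 3 diarrhea AL101 is interrupted and modified as Table 3 states. Limit the discretionary wording on reducing dose or frequency to events outside Table 3. Align the 14-day wording with Table 3.
4. Keep item 3's instruction to interrupt for any Grade 2 or 3 diarrhea not controlled with loperamide. Restricting it to related events would remove a safeguard for events judged unrelated. Keep the advice on 5 to 7 extra days and on corticosteroids.
5. State that the clinical-judgment sentence opening Section 6.4.2 applies to supportive care, not to Table 3's dose steps.

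The cost is one wording amendment, a site memo and slightly less site discretion over dosing. No patients, visits or analyses are added.
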